9.2.2 Relationship to Investigational Product

The investigator will be asked to document his/her opinion of the relationship of the adverse event to the investigational product as follows:

- Not related The event can be readily explained by the patient's underlying medical condition or concomitant therapy, and no relationship exists between the investigational product and the event.
- Unlikely related The temporal relationship between the event and the administration of the investigational product is uncertain, and the event can most likely be explained by the patient's medical condition or other therapies.
- Possibly related There is some logical temporal relationship between the event and the administration of the investigational product, and the event is unlikely to be explained by the patient's medical condition or other therapies.
- Related The temporal relationship is compelling between the administration of the investigational product, and the event cannot be explained by the patient's medical condition or other therapies.

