3.2 Background Information on Ciclesonide and Rationale for Use in COVID-19

Alvesco[®] (ciclesonide) Inhalation Aerosol is an inhaled corticosteroid that has been approved in the United States for the indication of maintenance treatment of asthma as prophylactic therapy in adult and adolescent patients 12 years of age and older (Alvesco[®] Inhalation Aerosol US prescribing information, 2019). Alvesco (ciclesonide) Inhalation Aerosol is administered by oral inhalation employing a pressurized metered-dose inhaler (MDI) and is available in 2 strengths (80 μ g/actuation and 160 μ g/actuation). Additional summary information regarding Alvesco (ciclesonide) Inhalation Aerosol is provided in the product labeling (Alvesco[®] Inhalation Aerosol US prescribing information, 2019).

Systemic glucocorticoid therapy is not currently indicated in patients with pneumonia or COVID-19 because of the potential for prolonging viral replication, as observed in patients with Middle East Respiratory Syndrome Coronavirus (CDC, 2020). However, inhaled glucocorticoids, such as ciclesonide, may demonstrate clinical benefit in patients with less severe symptoms of COVID-19 (Fu et al, 2020; Zhai et al, 2020).

Institut Pasteur Korea has recently identified ciclesonide as a potential candidate against COVID-19 infection based on a screening of approximately 3000 drugs. A total of 48 drugs were initially pre-selected based on an assay of SARS-CoV and were further tested for antiviral activity against SARS-CoV-2. Of these, 24 drugs (including ciclesonide) showed antiviral activity against SARS-CoV-2 (Jeon et al, 2020). This finding was corroborated in a recent publication by Matsuyama et al, 2020, in which it was reported that ciclesonide blocked SARS-CoV-2 replication in cultured cells at low concentrations. Furthermore, a small number

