9.4 Reporting Serious Adverse Events

All serious adverse events that occur during the course of the study from the time informed consent is signed and up to the patient's study completion or discontinuation, whether or not the event is considered causally related to the investigational product, must be reported by the investigator to the sponsor's safety reporting group as described in the Safety Reporting Instructions. In the event that the investigator becomes aware of a serious adverse event that occurred after the patient completes or discontinues from the study, and the serious adverse event is suspected to be related to investigational product, it must be reported to the sponsor's safety reporting group. Any special reporting requirements are described in the Safety Reporting Instructions.

All serious adverse events must be reported **within 24 hours** from the time when the investigator first becomes aware of the event. Serious Adverse Event Report Forms will be provided to each study site. Details on the process of reporting can be found in the Safety Reporting Instructions. The completed Serious Adverse Event Form should be sent to Premier Research by one of the following methods:

For all serious, unexpected adverse events potentially related to the use of the investigational product, Covis or its designee will notify the appropriate regulatory authorities and all participating investigators in accordance with ICH guidelines and local safety reporting requirements. It is the responsibility of the investigator to notify the Institutional Review Board (IRB) of all unexpected serious adverse drug reactions involving risk to human subjects in compliance with their IRB reporting requirements.

Each serious adverse event must be followed until its resolution or its resolution with sequelae. Any follow-up information to a serious adverse event must be reported to the sponsor within 24 hours of receipt of the new information.

The investigator must determine whether the clinical seriousness of the event warrants removal of the patient from the study. The investigator should, in any case, institute appropriate diagnostic and therapeutic measures and keep the patient under observation for as long as is medically indicated.

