10.8 Analysis of Safety Data

The incidence of adverse events will be summarized by Medical Dictionary for Regulatory Activities (MedDRA) body system classification and preferred term. All treatment-emergent adverse events will be summarized overall and for each body system and preferred term by treatment group, relationship to investigational product, and severity. For tabulations by severity, only a patient's most severe event within the category (eg, overall, body system, or preferred term) will be counted. "Treatment-emergent" will be defined as starting or worsening after the first dose of investigational product. If the start date is missing, the event is assumed to be treatment-emergent. All serious adverse events will be tabulated.

In order to understand specific adverse events of special interest (eg, oral candidiasis), analyses will be conducted to compare the treatment arms with respect to differences in cumulative incidence rates with accompanying confidence intervals. Details will be provided in the SAP.

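### The causality scale in section 9.2.2 has no clear grade for an event with plausible timing that COVID-19 could also explain, so events classed as drug-related may be under-counted

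*Combined protocol and SAP*

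**What the plan says.** Section 9.2.2 asks the investigator for an opinion on one of four grades. Each definition joins two conditions with *and*.

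- *Not related*: another cause readily explains the event, and there is no relationship with the product.
- *Unlikely related*: the timing condition is that "The temporal relationship between the event and the administration of the investigational product is uncertain"; another cause must also be the most probable explanation.
- *Possibly related*: the timing must be logical "and the event is unlikely to be explained by the patient's medical condition or other therapies".
- *Related*: compelling timing, and nothing else can explain the event.

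Causality is then used in three places. Section 10.8 summarizes treatment-emergent events "by treatment group, relationship to investigational product, and severity". Section 9.4 has the sponsor or its designee notify authorities and investigators of serious unexpected events that may be related to the product. Section 9.4 also requires a report of a serious adverse event learned of after the patient completes or discontinues only if "the serious adverse event is suspected to be related to investigational product".

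Section 9.1 counts worsening of the disease under study as an adverse event unless it lies within that patient's usual fluctuation. It also asks for every new infection to be recorded.

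**The concern.** A causality scale should give every event a grade, and its middle grade normally holds events for which both the drug and the disease are credible causes. Here the middle grade excludes them. In this trial they are foreseeable: every patient has symptomatic COVID-19, the product is taken twice daily for 30 days so on-treatment timing will often be plausible, and disease worsening is itself recorded as an adverse event. An investigator who must choose a grade for such an event may choose a lower one, and different investigators may choose differently.

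Two outputs are at stake: the count of events classed as drug-related in the section 10.8 breakdown, and the section 9.4 reports that depend on a judgement of causality. Section 9.4 does not say which of the four grades count as suspected or potential relatedness, so the link from grade to report is also left open.

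**Working it through.** The plan states no figure that depends on these definitions, so there is none to reproduce. The check is to apply the four definitions as written.

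**Test case: logical timing, and COVID-19 could equally explain the event.**

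| Grade | Timing condition | Other-cause condition | Fits? |
|---|---|---|---|
| *Related* | compelling: not met | nothing else can explain it: not met | No |
| *Possibly related* | logical: met | another cause is unlikely: not met | No |
| *Unlikely related* | uncertain: not met | another cause most likely: not met | No |
| *Not related* | none stated | readily explained otherwise, and no relationship exists | Only if the investigator asserts that there is no relationship |

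Making the timing compelling does not help, because *related* still fails on cause. Making COVID-19 the most likely cause does not help either, because *unlikely related* still fails on timing.

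**All combinations.** Cross four levels of timing with five levels of other cause. Treat the levels as nested, so that compelling timing is also logical, and a cause that cannot explain the event is also unlikely to. Use *not related* only where timing gives no link.

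| Timing | Cannot explain | Unlikely | Could equally | Most likely | Readily explains |
|---|---|---|---|---|---|
| None | no grade | no grade | no grade | no grade | *not* |
| Uncertain | no grade | no grade | no grade | *unlikely* | *unlikely* |
| Logical | *possibly* | *possibly* | no grade | no grade | no grade |
| Compelling | *possibly* and *related* | *possibly* | no grade | no grade | no grade |

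Combinations without a grade: 4 + 3 + 3 + 3 = 13 of 20. If the investigator may also assert no relationship for readily explained events with logical or compelling timing, the count is 13 − 2 = 11. These counts depend on how finely the grid is cut and say nothing about how many events fall in each cell. What does not depend on the grid is that, with plausible timing and a credible other cause, the only grade open is *not related*, and only on a positive assertion of no relationship. One cell meets two definitions, so a precedence rule is needed as well.

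**Size.** The documents give no adverse event rate and no share of events with two credible causes. As an illustration only, let N be the events with plausible timing that the product could have caused, and q the share that COVID-19 could also explain. If all of those are graded down, the count classed as possibly related or related is N(1 − q) instead of N, a fall of N − N(1 − q) = qN, or a fraction q. An assumed q of 10% to 70% gives a fall of 10% to 70%. The all-cause count in each arm is the same for any q.

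**The case against.** Four points stand against a broader claim.

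1. *The scale pushes these events down.* A reader might infer that the text assigns them to *unlikely related* or *not related*. It does not: the first needs uncertain timing and the second needs no relationship. Grading down is a plausible choice by an investigator who is asked for an opinion, not a rule in the text.
2. *Drug harm is under-counted.* The main safety analyses do not use the grade. Section 10.8 summarizes all treatment-emergent events overall, by body system and by preferred term, tabulates all serious adverse events, and compares cumulative incidence of special-interest events between arms. In a blinded, randomized, placebo-controlled trial, incidence by arm is the evidence on harm.
3. *The scale hides the harm the protocol itself fears.* Section 3.2 says a class of steroid is not indicated "because of the potential for prolonging viral replication", but says this of systemic therapy and then sets inhaled steroids apart. Worse COVID-19 is also measured without attribution, through hospital admission or death, mortality, oxygen saturation, symptoms and day 30 viral load (section 7.1.1).
4. *The grade controls serious-event reporting.* Section 9.4 sends every on-study serious event to the sponsor within 24 hours whatever its cause. Its causality phrases are not tied in the text to the section 9.2.2 grades, and the Safety Reporting Instructions, which hold further detail, are not among the documents.

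All four narrow the point. None closes the gap in section 9.2.2. The reporting after discontinuation also keeps some weight: section 5.3.4 follows only ongoing events after early termination, so a new serious event in a patient who leaves early must be reported under section 9.4 only if suspected to be related.

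**Conclusion.** The gap is real and follows from the wording alone. It may lower the number of events classed as drug-related in the by-relationship table, and may affect notification of serious unexpected events and reporting of serious events learned of after completion or discontinuation. It does not bias the all-cause comparison of adverse events by arm, the serious-event tables, the special-interest comparisons or on-study reporting to the sponsor.

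The size cannot be computed from the documents. That there is any effect rests on two assumptions: that events with two credible causes occur, which the population, dosing and section 9.1 make foreseeable, and that some investigators grade them down, which the documents neither require nor prevent. This is a worthwhile, inexpensive correction to definitions, not a threat to the trial's safety conclusions.

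**What to change.** In section 9.2.2, redefine the middle grade along these lines: *Possibly related: the timing relative to dosing is logical and the product could have caused the event, whether or not the patient's condition or another therapy could also explain it. An event that meets the conditions for Related is graded Related.*

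The *whether or not* matters. Wording that required another possible explanation would leave out events with logical timing that the disease is unlikely to explain, which are correctly graded *possibly related* now. A default for the remaining ungraded combinations, such as uncertain timing with no likely other cause, would complete the scale.

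In section 9.4, state that *possibly related* and *related* both count as potentially or suspected related. Carry the same wording into the eSource form and the Safety Reporting Instructions.

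The cost is a few sentences and matching form text, with no change to visits, sample size or analysis method. The drawback is that more events in both arms will be graded *possibly related* and the grade will discriminate somewhat less. Safety conclusions should therefore rest on all-cause incidence by arm.

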9.2.3 Action Taken with Investigational Product

For each recorded adverse event, the action taken with investigational product will be documented as follows:

- No change
- Drug interrupted
- Drug withdrawn
- Not applicable
- Unknown

9.2.4 Outcome

The outcome of the adverse event will be documented as follows:

- Recovered/resolved
- Recovered/resolved with sequelae
- Recovering/resolving
- Not recovered/not resolved
- Fatal
- Unknown

Outcome data will be obtained by qualified healthcare providers during the scheduled patient contacts and recorded in the eSource.

9.3 Serious Adverse Event Definition

A serious adverse event is any untoward medical occurrence that, at any dose:

- Results in death
- Is life-threatening
- Requires patient hospitalization or prolongation of existing hospitalization
- Results in persistent or significant disability and/or incapacity
- Results in a congenital anomaly or birth defect

The term "life-threatening" in the definition of "serious" refers to an event in which the patient was at immediate risk of death at the time of the serious adverse event. It does not refer to a serious adverse event that hypothetically might have caused death if it were more severe.

Medical and scientific judgment should be exercised in deciding whether expedited reporting is appropriate in other situations, such as important medical events that may not be immediately life-threatening or result in death or hospitalization, but may jeopardize the patient or may require intervention to prevent one of the other outcomes listed in the definition above. These should also be considered to be serious adverse events.

9.4 Reporting Serious Adverse Events

All serious adverse events that occur during the course of the study from the time informed consent is signed and up to the patient's study completion or discontinuation, whether or not the event is considered causally related to the investigational product, must be reported by the investigator to the sponsor's safety reporting group as described in the Safety Reporting Instructions. In the event that the investigator becomes aware of a serious adverse event that occurred after the patient completes or discontinues from the study, and the serious adverse event is suspected to be related to investigational product, it must be reported to the sponsor's safety reporting group. Any special reporting requirements are described in the Safety Reporting Instructions.

All serious adverse events must be reported **within 24 hours** from the time when the investigator first becomes aware of the event. Serious Adverse Event Report Forms will be provided to each study site. Details on the process of reporting can be found in the Safety Reporting Instructions. The completed Serious Adverse Event Form should be sent to Premier Research by one of the following methods:

For all serious, unexpected adverse events potentially related to the use of the investigational product, Covis or its designee will notify the appropriate regulatory authorities and all participating investigators in accordance with ICH guidelines and local safety reporting requirements. It is the responsibility of the investigator to notify the Institutional Review Board (IRB) of all unexpected serious adverse drug reactions involving risk to human subjects in compliance with their IRB reporting requirements.

Each serious adverse event must be followed until its resolution or its resolution with sequelae. Any follow-up information to a serious adverse event must be reported to the sponsor within 24 hours of receipt of the new information.

The investigator must determine whether the clinical seriousness of the event warrants removal of the patient from the study. The investigator should, in any case, institute appropriate diagnostic and therapeutic measures and keep the patient under observation for as long as is medically indicated.

10 STATISTICAL EVALUATION

As a companion to this protocol and in an effort to provide a more detailed explanation of the statistical methodology to be used for this study, a SAP will be finalized prior to locking the database and before unblinding the randomization. Any changes in the statistical methods described in this protocol that occur prior to unblinding will be documented in the SAP and will not require a protocol amendment.

10.1 Sample Size and Power

This study is designed to assess the efficacy and safety of ciclesonide MDI plus standard supportive care compared with placebo MDI plus standard supportive care. The primary endpoint is time to alleviation of COVID-19-related symptoms of cough, dyspnea, chills, feeling feverish, repeated shaking with chills, muscle pain, headache, sore throat, and new loss of taste or smell, defined as symptom-free for a continuous period of ≥ 24 hours (ie, ≥ 3 AM/PM assessments) by day 30. The Cox proportional hazards model will be used to compare treatment arms with respect to time to alleviation (or recovery) of COVID-19-related symptoms as defined in the primary endpoint. Total number of events (recoveries) as well as the expected rate of recovery (or hazard ratio) for treatment compared to placebo are key determinants of power. The expected median survival time is approximately 7 days for the ciclesonide arm and approximately 11 days for the placebo arm (hazard ratio of approximately 1.58) with a total study duration of 30 days. For 90% power, approximately 201 events (recoveries) are required to detect this anticipated increase in rate of recovery between ciclesonide and placebo. A sample size of 232 patients (116 per arm) is required to achieve the specified 90% power at an $\alpha = 0.05$ for this study. To account for an unknown drop-out rate in this patient population as well as other factors that may impact the overall power of the study, the planned sample size was increased to 400 patients (200 in each arm) for this study. Note that these are best estimates at this point as there is still much uncertainty regarding COVID-19.

10.2 Statistical Analysis Sets

The safety population will include all patients who received at least 1 dose of investigational product (either ciclesonide MDI or placebo MDI). Safety analyses will compare groups defined by the treatment they received. The ITT population will include all randomized patients. Analyses conducted on the efficacy dataset will be on an ITT basis where the treatment groups are defined by the treatment to which patients were randomized.

Any additional analysis sets will be defined in the SAP.

10.3 Statistical Methods

10.3.1 General Principles

Summary statistics will be presented by treatment group. For continuous variables, unless otherwise stated, the number of available observations (n), mean, standard deviation, median, and range will be provided. For categorical variables, the number and percentage in each category will be determined.

10.3.2 Missing Data

All attempts will be made to minimize the amount of missing data. Sensitivity analyses may be conducted to evaluate the potential impact of the missing data.

10.4 Demographic and Baseline Characteristics

Demographics and baseline characteristics, medical history, baseline physical examination findings, baseline vital sign data, baseline height, baseline weight, and baseline body mass index will be summarized descriptively by treatment group.

10.5 Patient Disposition

Patient disposition will be summarized, including the reasons for discontinuation. The number of patients in each analysis population will be displayed and an accounting of exclusions from each study population will be provided.

10.6 Concomitant Medications

Concomitant medications will be tabulated by Anatomical and Therapeutic Class of World Health Organization (WHO) drug, preferred term, and treatment group. A medication's usage will be considered concomitant if it was started or continued after administration of investigational product. If the start date is missing, it will be assumed that the medication was used concomitantly.

10.7 Analysis of Efficacy Data

10.7.1 Primary Efficacy Endpoint

The primary efficacy variable is time to alleviation of COVID-19-related symptoms of cough, dyspnea, chills, feeling feverish, repeated shaking with chills, muscle pain, headache, sore throat, and new loss of taste or smell, defined as symptom-free for a continuous period of \geq 24 hours (ie, \geq 3 AM/PM assessments) by day 30. The primary analysis will be based on the ITT population (all randomized patients). To improve the precision of treatment effect estimation and inference, baseline covariate adjustments will be made for gender, age, race, and body mass index, as these are known COVID-19 risk factors. A Cox proportional hazards model will be used to allow for inclusion of these additional covariates. The median time to event and 95% confidence intervals will be summarized by treatment arm, and Kaplan-Meier estimates of the survival curves will also be generated.

The SAP will describe how missing data will be handled in the primary analysis. In addition, a sensitivity analysis for the primary endpoint will be conducted using a tipping point analysis that will systematically and comprehensively vary assumptions about the missing outcomes on the treatment arms. Details will be provided in the SAP.

